8.5. Concomitant Medications

Concomitant medications are defined as medications taken during the treatment emergent period.

Concomitant medications will be summarized by the World Health Organization Drug Dictionary therapeutic class, pharmacological class, and preferred term. Concomitant use of CYP3A4 strong, moderate or weak inhibitors will be listed and/or summarized separately. The search for usage of CYP3A4 inhibitors will be based on, but not limited to the preferred terms in Appendix 1.

8.6. Study Drug Exposure

Ibrutinib and/or dexamethasone dose for a subject may be held and/or reduced according to the protocol specified criteria (see protocol Section 6.5).

For each subject the following parameters will be calculated when applicable.

- Treatment duration for each study drug (ibrutinib or dexamethasone) in month
- Time to addition of dexamethasone in month (Cohorts 1 and 3 only)
- Total cumulative dose administered for each study drug
- Average dose administered for each study drug

-
- Relative dose intensity for each study drug
 - Number of dose missed for each study drug
 - Number of dose reduction for each study drug
 - Ibrutinib dose interruption ≥ 7 consecutive days (yes or no)
 - Dexamethasone dose interruption ≥ 14 consecutive days (yes or no)

For each parameter, descriptive statistics (mean, standard deviation, median, and range for continuous variables; number and proportion for categorical variables) will be calculated by treatment cohort.

8.7. Subsequent Antineoplastic Therapy for Multiple Myeloma

Anti-myeloma treatments that started after discontinuation of study treatment (i.e. started after the last dose of study drug) will be considered as subsequent antineoplastic therapies for multiple myeloma. Subsequent antineoplastic therapies will be summarized by type (e.g. radiotherapy, systemic therapy, bone marrow or stem cell transplant) and preferred term.

8.8. Efficacy Analyses

Starting from Cycle 2, subjects will be evaluated by the investigators per the modified IMWG response criteria. Confirmation of investigator-assessed responses by an independent review committee (IRC) may be done as a supportive assessment. The method of independent review will be governed by an IRC charter, if needed. Some or all of the following assessments may be required to confirm the response categories: M-protein evaluations (UPEP and SPEP, serum and urine IFE, serum FLC), plasmacytoma evaluation, bone radiological assessment, bone marrow aspiration and biopsy, and serum chemistries including calcium and albumin.

The all treated population is the primary population for the efficacy endpoints. Unless specified otherwise, the all treated population will be used for all efficacy analyses. Response rates (CBR rate and ORR) will also be analyzed based on response evaluable population and will be considered as sensitivity analyses. Only adequate response assessments will be included in the analysis. An adequate response assessment is one for which the response assignment is sCR, CR, VGPR, PR, MR, SD or PD (i.e. not UE/Unknown).

IMWG criteria specify that all response categories require confirmation from a second consecutive assessment made at any time after the initial assessment with the exception of sCR and CR. The initial sCR or CR will be reported as confirmed response. However, if a subject has only one adequate post baseline assessment for which the response assignment is MR, PR or VGPR, then the best response will be summarized as SD.

In Cohorts 1 and 3, subjects will be on ibrutinib monotherapy and may convert to ibrutinib and dexamethasone combination therapy at the discretion of the investigator after a confirmed PD on ibrutinib monotherapy. Thus the efficacy endpoints (CBR, DCB, ORR, DOR, PFS, and TTP) will be presented and distinguished as with and without dexamethasone for subjects in Cohorts 1 and 3, when applicable.

No inferential statistical comparisons among treatment cohorts will be performed in this study.

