Progressive Disease (PD)	
Any one or more of the following:
 
 
• Increase of 25% from lowest value in g: 
 
▪ Serum M-component (absolute increase must be <math>\geq 0.5</math> g/dL)c
 
▪ Serum M-component increase <math>\geq 1</math> g/dL, if starting M component was <math>\geq 5</math> g/dL
 
▪ Urine M-component (absolute increase must be <math>\geq 200</math> mg/24 h)c
 
▪ If at on study, the only measurable non-bone marrow parameter was FLC, the difference between involved and uninvolved FLC levels (absolute increase must be <math>>10</math> mg/dL)c
 
▪ Bone marrow plasma cell percentage (absolute % must be <math>\geq 10\%</math>)c
 
 
 
 
Or any one or more of the following felt related to the underlying clonal plasma cell proliferative disorder
 
 
▪ Development of new soft tissue plasmacytomas or bone lesions
 
▪ Hypercalcemia (<math>\geq 11.5</math> mg/dL)
 

Relapse from CR or sCR d	
Subject who has achieved confirmed CR who has any one or more of the following:
 
 
• Reappearance of serum or urine M-protein by immunofixation or electrophoresis
 
• Development of <math>\geq 5\%</math> plasma cells in the bone marrow f
 
• Appearance of any other sign of progression (i.e., new plasmacytoma, lytic bone lesion, or hypercalcemia)
 

a All response categories require two consecutive assessments made at any time before the institution of any new therapy; complete response and PR, MR and SD categories also require no known evidence of progressive or new bone lesions if radiographic studies were performed. Radiographic studies are not required to satisfy these response requirements. Bone marrow assessments need not be confirmed.

b Presence/absence of clonal cells is based upon the k/ $\lambda$  ratio. An abnormal k/ $\lambda$  ratio by immunohistochemistry and/or immunofluorescence requires a minimum of 100 plasma cells for analysis. An abnormal ratio reflecting presence of an abnormal clone is k/ $\lambda$  of  $>4:1$  or  $<1:2$ .

c Positive immunofixation alone in a subject previously classified as CR will not be considered progression.

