### Confirmation of Response Categories

In order to be classified as a hematologic response, confirmation of serum monoclonal protein, serum immunoglobulin free light chain (when primary determinant of response) and urine monoclonal protein (when primary determinant of response) results must be made by verification on two consecutive determinations. Confirmation assessments may be performed at any time after the initial assessment.

- Bone marrow aspirate/biopsy is **only** required to document CR or sCR, except for subjects with bone marrow plasmacytosis evaluable disease **only**, where a bone marrow is required to document all response categories including progression. However, a second confirmatory bone marrow is not required to confirm response in any case
- Radiographic studies are not required to satisfy these response requirements; however, if radiographic studies were performed there should be no evidence of progressive or new bone lesions.

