8.8.1. Primary Efficacy Endpoint

The primary endpoint of the study is the CBR rate, defined as the proportion of subjects achieving a MR or better prior to initiation of new antineoplastic therapy as assessed by investigator per modified IMWG criteria.

The number and percent of subjects in each best response category (sCR, CR, VGPR, PR, MR, SD, PD) will be summarized by treatment cohort.

CBR rate and its corresponding 2-sided 90% exact binomial confidence interval (CI) will be calculated and presented by treatment cohort. For subjects in Cohorts 1 and 3, CBR will be calculated during ibrutinib monotherapy period (i.e. prior to addition of dexamethasone) as primary analysis. CBR across the whole study course (including ibrutinib and dexamethasone combination therapy period) will be calculated and presented as secondary analysis.

In addition, CBR rate will be analyzed based on response evaluable population and will be considered as sensitivity analyses.

Subgroup Analysis

Subgroup analyses may be performed for the following selected baseline characteristics and potential prognostic variables.

- Sex (male vs. female)
- Age (<65 vs. ≥65 years, <75 vs. ≥75 years)
- Race (Caucasian vs. non-Caucasian)
- Baseline ECOG score (0 vs. 1)
- Baseline hematologic abnormality (yes vs. no); hematologic abnormality: Hgb < 10 g/dL, platelets < $100 \times 10^9/L$ or ANC < $1 \times 10^9/L$
- Disease status (relapsed vs. relapsed and refractory)

-
- Number of prior systemic therapies (2-3 vs. ≥ 4)
 - Refractory status of last line of prior therapy (yes vs. no)
 - Refractory to prior immunomodulatory drugs (yes vs. no)
 - Refractory to prior proteasome inhibitors (yes vs. no)
 - Refractory to prior immunomodulatory drugs and proteasome inhibitors (yes vs. no)
 - FISH abnormalities
 - Del 17p (present vs. absent)
 - t(14;16) (present vs. absent)
 - t(4;14) (present vs. absent)
 - At least a presence of Del 17p, t(14;16) or t(4;14) vs. none of the three
 - Last prior treatment [(no PI/IMiD) vs. (PI or IMiD) vs. (PI and IMiD)]
 - Last prior treatment included PI (yes vs. no)
 - Last prior treatment included IMiD (yes vs. no)

CBR rate and its corresponding 2-sided 90% exact binominal CI will be calculated within each stratum of every subgroup. Forest plot will be provided for the subgroup analyses.

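### SAP 8.8 reports a single, unrepeated CR or sCR as confirmed; protocol Appendix 5 does not allow this and SAP section 10 does not declare it

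*SAP*

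**What the plan says.** SAP 8.8 attributes its confirmation rule to the IMWG criteria. It says each category needs a second consecutive assessment, "made at any time after the initial assessment with the exception of sCR and CR", and continues: "The initial sCR or CR will be reported as confirmed response". The one explicit downgrade, to stable disease (SD), applies "if a subject has only one adequate post baseline assessment for which the response assignment is MR, PR or VGPR".

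Protocol Appendix 5, footnote a, has no such exception: "All response categories require two consecutive assessments made at any time before the institution of any new therapy". The only relief it gives from repetition is "Bone marrow assessments need not be confirmed". The part of the appendix on confirming response categories says that the protein "results must be made by verification on two consecutive determinations". This covers serum M-protein, and also free light chain (FLC) or urine M-protein where that measure is the primary determinant of response. It again waives only the second marrow.

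SAP 8.8.1 defines the primary CBR as "defined as the proportion of subjects achieving a MR or better prior to initiation of new antineoplastic therapy as assessed by investigator", under the modified IMWG criteria. The SAP definitions of ORR, DCB (duration of clinical benefit) and DOR (duration of response) use the word *confirmed*; the CBR definition does not.

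**The concern.** The two documents give different answers for the same subject. By the protocol, a CR seen once and not repeated is not a confirmed CR. By the SAP, it is.

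The SAP rule is also uneven within itself. A subject whose only adequate post-baseline assessment is VGPR becomes SD and is a non-responder. If that single assessment is CR, the subject is a responder. The highest category therefore carries the lightest evidence requirement, in an open-label study with investigator-assessed response where independent review is optional (protocol 8.1.1).

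At stake are the labels in the best-response table and, in narrower circumstances, the numerators of ORR and CBR. The SAP introduction says that changes to the protocol's analysis plan are documented in the SAP. Section 10 lists two: the added time-to-benefit and time-to-response endpoints, and the major hemorrhage definition. The CR/sCR exemption is not among them.

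**Working it through.** **1. Does the marrow waiver cover the exemption?** No. Appendix 5 defines CR by negative serum and urine immunofixation, fewer than 5% marrow plasma cells and disappearance of soft tissue plasmacytomas, plus a normal FLC ratio where FLC was the only measurable non-marrow parameter. Waiving the repeat marrow leaves the other components subject to the rule that they "must be made by verification on two consecutive determinations". Other protocol text agrees. The Appendix 5 row on relapse from CR refers to a confirmed CR, and section 7.1.2 and Appendix 4 footnote u list CR and sCR among the categories to be confirmed.

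**2. Which endpoints change?** The table takes consecutive adequate assessments before any new therapy. I assume that an assessment at a higher category can serve as the second assessment for a lower one.

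| Sequence | SAP 8.8 as written | Appendix 5 | What differs |
|---|---|---|---|
| CR, CR | CR | CR | Nothing |
| VGPR, CR, VGPR | CR | VGPR | Best-response label only |
| MR, CR, MR | CR | MR | Label, ORR, DOR |
| SD, CR, SD | CR | SD | Label, ORR, DOR, CBR, DCB |
| SD, MR, SD | No explicit downgrade; only the general sentence applies | SD | CBR and DCB, if the general sentence is overlooked |

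The primary endpoint moves through the exemption only in the fourth pattern, where the CR or sCR has no assessment at MR or better beside it. The last row is a separate gap. The SD downgrade is written for subjects with one adequate post-baseline assessment, so an unrepeated MR followed by SD or PD depends on the general sentence alone.

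**3. Do the design figures depend on this?** Inputs are from protocol 8.5.1–8.5.2 and SAP 3.1–3.2. Cohorts 2–4 need at least 3 responders in 18, then at least 8 in 43, for 10% versus 25%. Cohort 1 needs at least 2 in 11, then at least 7 in 35, for 10% versus 30%.

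For Cohorts 2–4, with 43 − 18 = 25 subjects in stage 2:

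P(success at p) = Σ over x = 3 to 18 of C(18,x) pˣ (1−p)^(18−x) × P[Bin(25,p) ≥ 8−x]

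- Cohorts 2–4: 0.0480 at p = 0.10 and 0.8003 at p = 0.25 (stated: 5%, 80%).
- Cohort 1, same form: 0.0422 at p = 0.10 and 0.8510 at p = 0.30 (stated: 5%, 85%).
- Cohort 1 continuation at a true rate of 20%: 1 − 0.8¹¹ − 11 × 0.2 × 0.8¹⁰ = 0.678 (stated: about 0.68).

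All reproduce. Removing the exemption changes no sample size, limit, alpha or power.

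**4. Sensitivity, by assumption.** The documents do not say how many subjects would have an isolated CR or sCR as their sole response. Suppose such subjects added d points to a true confirmed CBR of 10%. Putting p = 0.10 + d into the formula gives:

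| d (points) | Cohorts 2–4 false-positive rate |
|---|---|
| 0 | 0.048 |
| 0.5 | 0.061 |
| 1 | 0.075 |
| 2 | 0.110 |

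One subject is 1/43 = 2.3 points. At the success limit, 8/43 = 18.6% (90% exact CI 9.6–31.1%) against 7/43 = 16.3% (7.9–28.4%).

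**The case against.** The strongest reply is that the primary endpoint is hardly exposed. CBR needs only MR or better, and myeloma proteins are measured at the start of each cycle (protocol 7.1.2, with visits every second cycle from Cycle 12). A subject who reaches CR will usually be at MR or better just before or just after, and so is already a confirmed clinical benefit responder. CR also rests on several findings, not one laboratory value. All of this stands, and it limits the point mainly to the CR/sCR rows and, less often, ORR and DOR.

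The SAP might also be following a published IMWG rule. That cannot be checked from these documents. It would not settle the matter, because the endpoint is tied to the protocol's own modified criteria, and those contain no CR exemption.

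A reader might infer more than the text supports:

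- *That the CBR sentence contradicts Appendix 5 because it omits the word confirmed.* It does not. The protocol's own CBR definition (4.2.1 and 8.3.2) omits the word too. Both definitions invoke the modified IMWG criteria, SAP 8.8 applies the second-assessment rule to MR, PR and VGPR, and the interim text in both documents expects the last clinical benefit responder to be confirmed. It is a drafting gap.
- *That every CR or sCR is affected.* A CR repeated at the next assessment is counted the same under both rules.
- *That the exemption altered, or will alter, a stage decision.* Nothing shows this. The one expansion reported as met, in Cohort 4, rested on 4 confirmed MRs against a limit of 3 (protocol 2.4.5). The comparison of 7/43 with 8/43 is hypothetical.
- *That Appendix 5 demands repeat serum, urine and FLC results in every case.* FLC and urine need repeating only where they are the primary determinant of response.

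**Conclusion.** The point holds as an undeclared conflict between SAP 8.8 and protocol Appendix 5 over confirming CR and sCR. Its surest effect is on labelling: an unrepeated CR or sCR would be reported as confirmed in the best-response table. ORR and DOR change only when no PR or better is otherwise confirmed. CBR and DCB change only when an isolated CR or sCR is the subject's sole assessment at MR or better.

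I expect that last case to be rare, but this is a judgement because the documents give no count. The false-positive rates above 0.048 in the working are conditional on an assumed frequency and are not estimates for this trial. Design alpha and power are as stated in the plan. The correction is worth making before the final analysis because the rule conflicts with the protocol, reaches the primary numerator in principle, and is cheap to put right.

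**What to change.** In SAP 8.8:

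- Delete the CR/sCR exception and the sentence that reports the initial one as confirmed.
- Require verification on two consecutive determinations as in Appendix 5: serum M-protein, and FLC or urine M-protein where it is the primary determinant of response. State that no repeat marrow is needed.
- Classify any response not confirmed at the next adequate assessment at the best lower category that is confirmed. Apply this to MR, PR and VGPR as well as CR and sCR, and not only to subjects with a single post-baseline assessment.

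In SAP 8.8.1, define CBR as *confirmed MR or better*, to match ORR, DCB and DOR. This is a clarification, not the correction of a contradiction.

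The cost is a few sentences. No new procedure is needed, since Appendix 5 already asks for the repeat and myeloma protein tests are already scheduled. CR, ORR or CBR counts may fall slightly.

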8.8.1. Primary Efficacy Endpoint

The primary endpoint of the study is the CBR rate, defined as the proportion of subjects achieving a MR or better prior to initiation of new antineoplastic therapy as assessed by investigator per modified IMWG criteria.

The number and percent of subjects in each best response category (sCR, CR, VGPR, PR, MR, SD, PD) will be summarized by treatment cohort.

CBR rate and its corresponding 2-sided 90% exact binomial confidence interval (CI) will be calculated and presented by treatment cohort. For subjects in Cohorts 1 and 3, CBR will be calculated during ibrutinib monotherapy period (i.e. prior to addition of dexamethasone) as primary analysis. CBR across the whole study course (including ibrutinib and dexamethasone combination therapy period) will be calculated and presented as secondary analysis.

In addition, CBR rate will be analyzed based on response evaluable population and will be considered as sensitivity analyses.

Subgroup Analysis

Subgroup analyses may be performed for the following selected baseline characteristics and potential prognostic variables.

- Sex (male vs. female)
- Age (<65 vs. ≥65 years, <75 vs. ≥75 years)
- Race (Caucasian vs. non-Caucasian)
- Baseline ECOG score (0 vs. 1)
- Baseline hematologic abnormality (yes vs. no); hematologic abnormality: Hgb < 10 g/dL, platelets < $100 \times 10^9/L$ or ANC < $1 \times 10^9/L$
- Disease status (relapsed vs. relapsed and refractory)

-
- Number of prior systemic therapies (2-3 vs. ≥ 4)
 - Refractory status of last line of prior therapy (yes vs. no)
 - Refractory to prior immunomodulatory drugs (yes vs. no)
 - Refractory to prior proteasome inhibitors (yes vs. no)
 - Refractory to prior immunomodulatory drugs and proteasome inhibitors (yes vs. no)
 - FISH abnormalities
 - Del 17p (present vs. absent)
 - t(14;16) (present vs. absent)
 - t(4;14) (present vs. absent)
 - At least a presence of Del 17p, t(14;16) or t(4;14) vs. none of the three
 - Last prior treatment [(no PI/IMiD) vs. (PI or IMiD) vs. (PI and IMiD)]
 - Last prior treatment included PI (yes vs. no)
 - Last prior treatment included IMiD (yes vs. no)

CBR rate and its corresponding 2-sided 90% exact binominal CI will be calculated within each stratum of every subgroup. Forest plot will be provided for the subgroup analyses.

8.8.2. Secondary Efficacy Endpoints

8.8.2.1. Duration of Clinical Benefit (DCB)

For all cohorts, DCB will be computed for those subjects with confirmed responses (MR or better) prior to initiation of new antineoplastic therapy. DCB will be calculated from the first observation of response (before confirmation) to the time of PD (earliest occurrence), with death from causes other than progression censored.

PD based upon changes in monoclonal protein levels requires confirmation. No minimal time interval between assessments is stipulated. PD based upon bone marrow, bone lytic lesions, or plasmacytoma changes, or upon development of hypercalcemia attributed to multiple myeloma do not require confirmation. DCB will be right-censored for subjects who meet one or more of the censoring conditions listed in Table 4 below.

Similarly, for Cohorts 1 and 3 ibrutinib monotherapy, DCB will be computed for those subjects with confirmed responses (MR or better) prior to initiation of dexamethasone or new antineoplastic therapy, whichever occurs first.

Table 4: Date of Event and Censoring Rules for DCB Analysis

Row	Situation	Date of Event or Censoring	Outcome
Events include death due to progression or first documentation of confirmed PD that occurred on or prior to the data analysis cutoff date. For Cohorts 1 and 3 ibrutinib monotherapy, events need to meet one additional criterion: occurred at or prior to initiation of dexamethasone.			
1.1	Death due to progression or confirmed PD documented at scheduled disease assessments or between two scheduled disease assessments.	Earliest date of adequate disease assessment documenting confirmed PD or date of death due to progression, whichever occurs first.	Progressed
1.2	Death before first disease assessment	Date of death	Progressed
All other cases will be censored as follows:			
2.1	No baseline assessment	Date of first study treatment	Censored
2.2	No adequate post-baseline assessment (including lost to follow-up since enrollment)	Date of first study treatment	Censored
2.3	Not known to have confirmed PD or died due to progression at the data analysis cutoff date (this includes subjects who were known to have confirmed PD or died after the data analysis cutoff date)	Date of last adequate disease assessment showing no evidence of confirmed PD on or before data analysis cutoff date	Censored
2.4	Addition of dexamethasone (Cohorts 1 and 3 ibrutinib monotherapy only)	The start date of dexamethasone	Censored
2.5	Death from causes other than progression	Date of death	Censored

For subjects who meet more than one censoring condition, DCB will be censored according to the earliest censoring condition. For subjects who meet none of the censoring conditions, DCB will be calculated using the earliest event date.

$$\text{DCB Event (day)} = \text{Date of event} - \text{Date of first overall response}$$

$$\text{DCB Censor (day)} = \text{Date of censoring} - \text{Date of first overall response} + 1$$

Kaplan-Meier curves will be used to estimate the distribution of DCB. The 50th percentile of Kaplan-Meier estimates will be used to estimate the median DCB. A 2-sided 95% CI will be provided for this estimate. For the cases in which the median is not reached as if the study closure, the 25th percentile and its 2-sided 95% CI will be provided.

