5.7. Treatment-Emergent Period

The treatment-emergent period is defined as the period of time from the date of the first dose of study drug through 30 days after the date of the last dose of study drug (ibrutinib or dexamethasone) or the day before initiation of any subsequent anti-myeloma therapy, whichever occurs first.

The treatment-emergent period for monotherapy (Cohorts 1 and 3 only) is defined as the period of time from the date of the first dose of ibrutinib through 30 days after the date of the last dose of ibrutinib, or the day before the addition of dexamethasone, or the day before initiation of any subsequent anti-myeloma therapy, whichever occurs first.

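### Whole-course DCB and DOR in Cohorts 1 and 3 come out negative for a subject who first responds on added dexamethasone; three smaller wording conflicts sit in the same event and censoring tables

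*SAP*

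**What the plan says.** **Who is in the whole-course analysis.** SAP 5.7 treats added dexamethasone as study drug: "the last dose of study drug (ibrutinib or dexamethasone". SAP 8.8 lets Cohort 1 and 3 subjects add it after confirmed PD on monotherapy, and asks for DCB, DOR, PFS and TTP with and without it. For the primary endpoint, SAP 8.8.1 adds: "CBR across the whole study course (including ibrutinib and dexamethasone combination therapy period) will be calculated and presented as secondary analysis". SAP 8.8.2.1 then sets the DCB population: "For all cohorts, DCB will be computed for those subjects with confirmed responses (MR or better) prior to initiation of new antineoplastic therapy". The same section names dexamethasone separately from new antineoplastic therapy, so adding dexamethasone does not remove a subject.

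**How the duration is measured.** "DCB will be calculated from the first observation of response (before confirmation) to the time of PD (earliest occurrence". The Table 4 header likewise takes the first documentation of confirmed PD as the event. The formula is event date minus date of first response. SAP 8.8.2.3 applies the same rules to DOR but points to Table 3, which is the ECOG/Karnofsky conversion.

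**The other table entries.**
- Table 5 (PFS), row 1.1, takes any death as an event, but its date cell covers only PD or death due to progression.
- SAP 8.8.3.2 (TTP) censors deaths from other causes, yet borrows Table 4. Row 1.2 of that table, "Death before first disease assessment", is coded as progressed with no limit on cause.
- The sentence before Table 4 reads: "DCB will be right-censored for subjects who meet one or more of the censoring conditions listed in Table 4 below". The sentence after it uses event dates only for subjects who meet no censoring condition. Inside the table, the censoring rows are introduced by "All other cases will be censored as follows", and the event header says: "For Cohorts 1 and 3 ibrutinib monotherapy, events need to meet one additional criterion: occurred at or prior to initiation of dexamethasone". Table 5 follows the same pattern.

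**The concern.** DCB and DOR are secondary endpoints. A negative duration cannot enter a Kaplan-Meier estimate. Whoever programs the whole-course analysis would have to drop these responders or choose a rule on the spot, in an open-label study with the data in view. These are also the subjects for whom dexamethasone was added: Protocol 2.5 gives the aim as short-term stabilization so that slower responses can emerge. The other three entries mainly touch exploratory PFS and TTP, where two programmers could code the same subject differently.

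**Working it through.** **The plan's own figures.** The time-to-event rules carry no stated sample size or power, so only the Simon designs can be reproduced. Success probability is the sum, over Stage 1 counts x that pass, of P(X₁ = x) × P(Stage 2 supplies the remaining responses).
- Cohort 1 (≥2 of 11, then ≥7 of 35): 0.042 at a 10% rate and 0.851 at 30%. The chance of continuing at 20% is 0.678. The plan states 5%, 85% and about 0.68.
- Cohorts 2 to 4 (≥3 of 18, then ≥8 of 43): 0.048 at 10% and 0.800 at 25%. The plan states 5% and 80%.

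These figures use binary response only. For Cohorts 1 and 3, SAP 1.3 and 8.8.1 count responses before dexamethasone. No DCB, DOR, PFS or TTP rule enters.

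**(a) Whole-course DCB and DOR.** The documents give no subject-level dates, so take a hypothetical Cohort 3 subject with day 1 as first dose: confirmed PD first documented on day 57 (Cycle 3 Day 1), dexamethasone from day 64, confirmed MR first seen on day 113 (Cycle 5 Day 1), and a further confirmed PD on day 211.
- As written: 57 − 113 = **−56 days**.
- With the event taken as the first confirmed PD after the response: 211 − 113 = **+98 days**.
- If the first response comes k cycles after PD, the written rule gives 57 − (57 + 28k) = −28k days, so −28 to −168 days for k = 1 to 6.

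No other row resolves this. Row 2.3 needs a subject not known to have confirmed PD, and this one is. Row 2.4 is for the monotherapy analysis only. DOR behaves the same way for a first PR on added dexamethasone.

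*How many.* Protocol 2.4.5 reports 13 subjects in Cohort 1 and 18 in Cohort 3 at Stage 1, so at most 13 + 18 = 31. The documents do not say how many added dexamethasone or then responded.

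**(b) PFS date cell.** Suppose the last assessment without PD is on day 85 and death from another cause is on day 101. The PFS definition makes this an event at 101 − 1 = 100 days. Table 5 row 1.1 accepts the death but supplies no date for it, and row 2.3 excludes a subject known to have died.

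**(c) Early death in TTP.** Take a death from another cause on day 20, before any post-baseline assessment. The possible codings are:
- row 1.2: event at 20 − 1 = 19 days;
- row 2.2: censored at 1 − 1 + 1 = 1 day;
- row 2.5: censored at 20 − 1 + 1 = 20 days.

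The TTP definition rules out the first. The case needs a death within about the first four weeks, so it should be rare.

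**(d) Precedence.** For the subject in (a), monotherapy PFS is an event at 57 − 1 = 56 days by the Table 5 header. Under row 2.4 and the surrounding sentences read in isolation, it is censored at 64 − 1 + 1 = 64 days.

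**The case against.** **On (a).** A sensible programmer would take PD to mean PD after the response. That is probably what was meant, but the SAP specifies the earliest occurrence in the text and the first documentation in Table 4, and nowhere limits it to PD after response. One could also doubt that a response after PD counts at all. Yet the whole-course CBR in SAP 8.8.1 can differ from the monotherapy CBR only if such responses count. A small limit does stand: Protocol 6.3.3.1 lets dexamethasone start once repeat samples are collected, so in a few subjects the PD may not be confirmed at that point.

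**On (b) to (d).** Here the objection largely succeeds. The PFS definition and the Table 5 header supply the date of death. Row 1.2 sits under a header limited to death due to progression, and the TTP definition censors other deaths. The censoring rows apply to the cases left over after the events, so the surrounding sentences can be read consistently with the tables. What remains is wording that should not need interpretation.

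**Two stronger readings a reader might infer.** First, that monotherapy PFS and TTP will be inflated because progressors are censored when dexamethasone starts. The documents do not support this: the headers count those progressions as events, and dexamethasone uptake is not given, so any size would rest on assumed inputs. Second, that row 2.5 (censor at death from other causes) ought to override rows 2.2 and 2.3, because under the earliest-condition rule it never sets the date. Row 2.5 is redundant, but the result is coherent. After stopping treatment without PD, subjects are seen about every 2 months with tests at the investigator's discretion (Protocol 7.1.4), and after progression or new therapy contact is for survival and further treatment (Protocol Appendix 4). The gap between last assessment and death therefore has no firm bound, and censoring at death would credit unassessed time as progression-free. That is a trade-off, not an error.

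**Conclusion.** Point (a) is wrong as written. For any Cohort 1 or 3 subject whose first response follows dexamethasone added for confirmed PD, the whole-course DCB or DOR formula gives a negative number. The −56 days is illustrative. The count is unknown; the ceiling of 31 assumes no enrolment in these two cohorts beyond the Stage 1 numbers in Protocol 2.4.5. The Table 3 citation for DOR is a plain cross-reference error. Points (b), (c) and (d) are real conflicts of wording whose intent can be recovered from the definitions and headers, and no size is claimed for them.

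Overall severity is minor to moderate: only secondary and exploratory endpoints are affected, and SAP 8.8 plans no inferential comparison between cohorts. It would be a mistake to infer that the primary result is in doubt, because CBR and the expansion decisions use none of these rules. Cohorts 2 and 4 receive dexamethasone from Cycle 1, so (a) and row 2.4 do not reach them.

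**What to change.** - **(a)** For DCB and DOR only, define the event as the first confirmed PD, or death due to progression, after the response being timed. Put the same qualifier in row 2.3 for DCB and DOR, but not for TTP, which shares Table 4 and times no response. In SAP 8.8.2.3, change the reference from Table 3 to Table 4.
- **(b)** In Table 5 row 1.1, make the date cell refer to the date of death from any cause.
- **(c)** For TTP, limit row 1.2 to deaths due to progression and let the existing censoring rows handle other deaths.
- **(d)** In the sentences around Tables 4 and 5, state that event rows take precedence over censoring rows, and that row 2.4 applies only when there is no confirmed PD at or before the start of dexamethasone.

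The order among rows 2.2, 2.3 and 2.5 can stay as it is. The cost is SAP wording and programming. No data collection, visit or treatment changes.
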